11. INTERIM ANALYSES AND DATA MONITORING

No interim analyses are planned for this study. The Data and Safety Monitoring Board (DSMB) will monitor safety throughout the study. The DSMB will be independent of the Sponsor, CRO, and the investigators and will be empowered to recommend stopping the study due to safety concerns. The membership of the DSMB and its mandate will be described in a separate DSMB charter.

12. CHANGES TO STUDY CONDUCT OR ANALYSES PLANNED IN THE PROTOCOL

12.1 Changes in the Conduct of the Study

No changes are planned as of the date of the SAP.

12.2 Changes in the Analysis Planned in the Protocol

No changes are planned as of the date of the SAP.

14. APPENDICES

14.1 Schedule of Events

Procedures	Screening				Double-blind Period		End of Study -
	Clinic Visit	Telephone Contact	Practice Laboratory Classroom Session	Telephone Contact	First Laboratory Classroom Day	Second Laboratory Classroom Day	
	Visit 1	Visit 2		Visit 3	Visit 4	Visit 5	Visit 6
	Day -35 to -10	Day -9 to -8	Day -7	Day -1	Day 1	Day 15	Day 21 ^a (± 2)
Obtain informed consent	X						
Obtain informed assent	X						
Inclusion/Exclusion criteria	X	X	X	X	X		
Randomization						X	
Dispense study drug						X	
Study drug accountability							X
Medical History	X						
Psychiatric History	X						
Prior/concomitant medication review	X	X	X	X	X	X	X
K-SADS-PL	X						
Physical examination	X						X
Neurological examination	X						X
Height	X						
Weight (including body mass index)	X				X	X	X
Vital signs	X		X		X ^b	X ^b	X
Electrocardiogram (ECG)	X						X
Adverse event monitoring ^f						X	X
Columbia Suicide	X		X		X	X	X

Procedures	Screening				Double-blind Period		End of Study
	Clinic Visit	Telephone Contact	Practice Laboratory Classroom Session	Telephone Contact	First Laboratory Classroom Day	Second Laboratory Classroom Day	-
	Visit 1	Visit 2		Visit 3	Visit 4	Visit 5	Visit 6
Day -35 to -10	Day -9 to -8		Day -7	Day -1	Day 1	Day 15	Day 21 ^a (± 2)
Severity Rating Scale (C-SSRS)							
ADHD-RS-IV HV	X	X ^g		X			X
Classroom Practice Session ^c			X				
SKAMP ^d					X	X	
Math pretest for determination of math level	X						
PERMP ^d					X	X	
Dosing diary distribution/review					X	X	
Hematology/Chemistry	X						X
TSH	X						
Serum β-hCG (in females ≥ 8 years of age) ^e	X						X
Urinalysis	X						X
Urine drug screen	X				X	X	X
Urine β-hCG (in females ≥ 8 years of age) ^e					X	X	

Abbreviations: ADHD-RS-IV HV = ADHD Rating Scale Version IV Home Version (modified for investigator administration), β-hCG = beta-human chorionic gonadotropin, K-SADS-PL = Schedule for Affective Disorders and Schizophrenia for School-Age Children- Present and Lifetime version, PERMP = Permanent Product Measure of Performance, SKAMP = Swanson, Kotkin, Agler, M-Flynn, and Pelham Scale, TSH = thyroid stimulating hormone

^a Seven (± 2) days after the last dose of study drug, all subjects will return to the clinic and complete assessments.

^b Heart rate and blood pressure will be measured at approximately the same time on Day 1 and Day 15.

^c Including practice SKAMP assessments, practice PERMP tests, and other planned activities intended to familiarize subjects with the classroom setting.

^d Classroom sessions will be started at approximately 8 AM, 10 AM, 12 PM, 2 PM, 4 PM, 6 PM, and 8 PM.

^e Any positive urine β-hCG test should be confirmed by serum β-hCG.

^f Pre-treatment events will be collected from the time of informed consent until the first study drug administration.

^g If the parent/legal guardian cannot be reached, these assessments may be performed on Day -7.

14.2 Sample Laboratory Classroom Day Schedule

Nominal Time	Actual Time	Arrival	PERMP/SKAMP	Meal/snack	Dismissal
	6:30 am	X			
	7:30 am			X	
12 h postdose	8:00 am		X		
	9:45 am			X	
14 h postdose	10:00 am		X		
16 h postdose	12:00 pm		X		
	12:30 pm			X	
18 h postdose	2:00 pm		X		
	2:30 pm			X	
20 h postdose	4:00 pm		X		
22 h postdose	6:00 pm		X		
	6:30 pm			X	
24 h postdose	8:00 pm		X		
	8:45 pm				X

14.3 SKAMP Rating Scale and Subscales

Subscale	Item
Attention	1. Getting started on assignments for classroom periods
	2. Sticking with tasks or activities for the allotted time
	3. Attending to an activity or a discussion of the class
	4. Stopping and making transition to the next period
Deportion	5. Interacting with other children (e.g., other students)
	6. Interacting with adults (e.g., teacher or aide)
	7. Remaining quiet according to classroom rules
	8. Staying seated according to classroom rules
Quality of Work	9. Completing assigned work
	10. Performing work accurately
	11. Being careful and neat while writing or drawing
Compliance	12. Complying with teacher's usual requests or directions
	13. Following the rules established for the classroom

14.4 Laboratory Criteria for Markedly Abnormal Values

Parameter (Unit)	Markedly Abnormal Range (Conventional Unit)	Conversion Factor (Conventional to SI) / SI unit	SI Unit Markedly Abnormal Range
Hematology			
Hemoglobin (g/dL)	Female: ≤ 9.5, Male: ≤ 11.5 ≥ 17.2	10 / g/L	Female: ≤ 95 g/L, Male: ≤ 115 g/L, ≥ 172 g/L
Haematocrit (fraction, %)	≤ 30, ≥ 50	1 / %	≤ 30, ≥ 50 (1)
WBC ($10^3/\mu\text{L}$)	≤ 2.8, ≥ 16	$1 / \times 10^9/\text{L}$ (PPD Conv unit K/cu mm)	≤ 2.8, ≥ 16
RBC ($10^6/\mu\text{L}$)	≤ 3.0, ≥ 6.0	$1 / \times 10^{12}/\text{L}$ (PPD Conv unit $\times 10^6/\text{cu mm}$)	≤ 3.0, ≥ 6.0
Platelet Count ($10^3/\mu\text{L}$)	≤ 100, ≥ 500	$1 / \times 10^9/\text{L}$ (PPD Conv unit K/cu mm)	≤ 100, ≥ 500
Eosinophils (%)	≥ 10	1 / %	≥ 10
Neutrophils (%)	≤ 15	1 / %	≤ 15
Clinical Chemistry			
ALP (U/L)	≥ 3 x ULN	1 / U/L	≥ 3 x ULN
ALT (U/L)	≥ 2 x ULN	1 / U/L	≥ 2 x ULN
AST (U/L)	≥ 2 x ULN	1 / U/L	≥ 2 x ULN
Total Bilirubin (mg/dL)	≥ 2.0	17.1 / $\mu\text{mol}/\text{L}$	≥ 34.2
Albumin (g/dL)	< 50% LLN	10 / g/L	< 50% LLN
Creatinine (mg/dL)	≥ 2.0	88.4 / $\mu\text{mol}/\text{L}$	≥ 176
Creatine Phosphokinase (CPK) (U/L)	≥ 450	1 / U/L	≥ 450
LDH (U/L)	≥ 3 x ULN	1 / U/L	≥ 3 x ULN
GGT (U/L)	≥ 150	1 / U/L	≥ 150
Sodium (mEq/L)	≤ 130, ≥ 150	1 / mmol/L	≤ 130, ≥ 150
Potassium (mEq/L)	≤ 3, ≥ 5.5	1 / mmol/L	≤ 3, ≥ 5.5
Bicarbonate (mEq/L)	< 18, > 30	1 / mmol/L	< 18, > 30
Calcium (mg/dL)	< 8.4, or > 11.5	0.25 / $\mu\text{mol}/\text{L}$	< 2.1, or > 2.8
Chloride (mEq/L)	< 90, > 115	1 / mmol/L	< 90, > 115
Blood Urea Nitrogen (mg/dL)	≥ 30	0.357 / $\mu\text{mol}/\text{L}$	> 10.7
Glucose (fasting) (mg/dL)	≤ 45, ≥ 126	0.05551 / $\mu\text{mol}/\text{L}$	≤ 2.5, ≥ 11.1
Glucose (random) (mg/dL)	≤ 45, > 200	0.05551 / $\mu\text{mol}/\text{L}$	≤ 2.5, ≥ 11.1
Urinalysis			
RBC (hpf)	> 15	N/A	> 15
WBC (hpf)	> 15	N/A	> 15

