8.6 Clinical Laboratory Evaluations

The following laboratory tests will be performed at Screening (Visit 1) and EOS (Visit 6):

- Clinical Chemistry: Alanine aminotransferase (ALT), Alkaline Phosphatase (ALP), Aspartate aminotransferase (AST), Bicarbonate (HCO₃), Bilirubin (Total, Direct, Indirect), Blood Urea Nitrogen (BUN), Calcium (Ca), Chloride (Cl), Creatinine, Glucose, Magnesium (Mg), Phosphorus (P), Potassium (K), Protein (Total), Sodium (Na), Uric Acid, Albumin

- Hematology: Hemoglobin, Hematocrit, Platelet Count, RBC Count, WBC - Total Count, WBC Differential, (Basophils, Eosinophils, Lymphocytes, Monocytes, Neutrophils)
- Urinalysis: Blood, Glucose, Ketones, Leukocyte esterase, Microscopic examination, Nitrites, pH, Protein

Summary statistics for these laboratory panels (clinical chemistry, hematology and urinalysis) will be provided by treatment group and visit. Laboratory data will also be summarized in shift tables presenting summary statistics of raw data and change from baseline values (means, standard deviations, medians, ranges). All clinical laboratory assessments will be listed for each panel.

In addition, the incidence of markedly abnormal post-baseline laboratory values (MAPLV) will be presented to examine the frequency and percentage of subjects that have values that are potentially clinically significant (PCS). These criteria are outlined in Appendix 14.4.

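### SAP Appendix 14.4: the SI upper limit for fasting glucose does not match its conventional limit, and the SAP does not say which unit column governs the flags

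*SAP*

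**What the plan says.** SAP Section 8.6 states that "the incidence of markedly abnormal post-baseline laboratory values (MAPLV) will be presented" and refers to Appendix 14.4 for the criteria. It does not say whether the flags are derived from the conventional or the SI column.

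The entries in Appendix 14.4 that matter here are:

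- **Fasting glucose**, the row labelled "Glucose (fasting) (mg/dL": ≤ 45 or ≥ 126 mg/dL, factor 0.05551, SI limits ≤ 2.5 or ≥ 11.1.
- **Random glucose**, the next row: ≤ 45 or > 200 mg/dL, same factor, SI limits again ≤ 2.5 or ≥ 11.1.
- **Calcium**: < 8.4 or > 11.5 mg/dL, factor 0.25, SI limits < 2.1 or > 2.8.

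SAP Section 8.6 schedules chemistry at Screening and End of Study only, so each child has one scheduled post-baseline result. Neither the laboratory and visit sections of the protocol (11.4.2, 11.5.1.1, 11.5.3 and Appendix III) nor SAP Section 8.6 says whether blood is drawn fasting.

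**The concern.** A two-column threshold table is safe only if both columns state the same rule. For fasting glucose they do not. The conventional limits separate fasting from random samples (126 against 200 mg/dL), while the SI limits are identical, so the distinction disappears in SI units. The same result could count as markedly abnormal in one column and not in the other.

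What is at stake is whether a pre-specified safety count has one answer. With a single scheduled post-baseline chemistry sample, a value that is not flagged at End of Study has no later scheduled result to bring it into the table.

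**Working it through.** **Inputs.** All limits and factors come from SAP Appendix 14.4.

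**Formulas.** Expected SI limit = conventional limit × factor. Back-conversion = printed SI limit ÷ factor. Both were applied to every numeric limit whose factor is not 1.

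| Limit | Conventional | Factor | Expected SI | Printed SI | Difference | Printed SI converted back |
|---|---|---|---|---|---|---|
| Hemoglobin low, female | 9.5 | 10 | 95 | 95 | 0 | 9.5 |
| Hemoglobin low, male | 11.5 | 10 | 115 | 115 | 0 | 11.5 |
| Hemoglobin high | 17.2 | 10 | 172 | 172 | 0 | 17.2 |
| Total bilirubin | 2.0 | 17.1 | 34.2 | 34.2 | 0 | 2.0 |
| Creatinine | 2.0 | 88.4 | 176.8 | 176 | −0.45% | 1.99 |
| Calcium low | 8.4 | 0.25 | 2.1 | 2.1 | 0 | 8.4 |
| **Calcium high** | 11.5 | 0.25 | 2.875 | 2.8 | **−2.6%** | 11.2 |
| BUN | 30 | 0.357 | 10.71 | 10.7 | −0.09% | 29.97 |
| Glucose low, both rows | 45 | 0.05551 | 2.498 | 2.5 | +0.08% | 45.04 |
| **Fasting glucose high** | 126 | 0.05551 | 6.994 | 11.1 | **+58.7%** | 199.96 |
| Random glucose high | 200 | 0.05551 | 11.102 | 11.1 | −0.02% | 199.96 |

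**The table's method reproduces.** Hemoglobin, bilirubin and low calcium convert exactly. BUN, low glucose and random glucose agree to the printed decimals. The low fasting-glucose limit converts correctly with the same factor, so the mismatch in that row lies in the upper pair and not in the factor.

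**Fasting glucose.** No rounding turns 6.994 into 11.1. The values on which the columns disagree run from 126 to just under 200 mg/dL (6.99 to just under 11.1 in SI): flagged in conventional units, not flagged in SI.

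**Calcium.** 2.875 rounds to 2.88 or 2.9; only truncation gives 2.8. With finely reported SI results, values above 11.2 and up to 11.5 mg/dL are flagged in SI only, the opposite direction to glucose. If SI results were rounded to one decimal, the first flagged value would be 2.9, which starts at 2.85, or 2.85 ÷ 0.25 = 11.4 mg/dL. The gap then shrinks to about 0.1 mg/dL. The documents do not give the reporting precision.

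**Inequality signs.** Random glucose changes from > 200 to ≥ 11.1, so exactly 200 mg/dL (11.102) is flagged in SI only. BUN changes from ≥ 30 to > 10.7; exactly 30 mg/dL (10.71) is flagged either way.

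**The case against.** The strongest reply is that the error may never act. No section requires fasting samples. If all samples are treated as random, the random-glucose row applies, and its SI limit agrees with its conventional limit to rounding. Protocol Section 11.4.2 has the tests run centrally, so mixed units within the trial are unlikely, although Section 16.6 allows a local laboratory by exception. If only conventional units are programmed, the SI entries do nothing. This stands as a limit on impact. It does not make the fasting row correct, and the SAP does not close off either route.

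A high glucose would also stay visible elsewhere. SAP Section 8.6 provides summary statistics, shift tables and listings of all laboratory results, and under Protocol Section 12.2 the investigator judges each out-of-range value and records clinically significant ones as adverse events. That stands too: only the count in the incidence table could change.

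Three stronger readings are tempting, and the documents do not support them:

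- **That high fasting glucose will be missed.** This needs both fasting classification and use of the SI column, and neither is stated.
- **That the random-glucose limit was copied into the fasting row.** The match at 200 mg/dL makes this plausible, but it is an inference. Nor does any section say that the conventional column is the intended one.
- **That the SI units are wrong for calcium, BUN and glucose.** The text available to us shows micromol/L where the factors give mmol/L. That may come from reading the PDF by program, and the numerical mismatch does not depend on it.

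**Conclusion.** The fasting-glucose mismatch is certain as arithmetic: 6.99 by the table's own factor against a printed 11.1, and nothing elsewhere in the documents corrects it. Its effect on the results is conditional. A difference in the count arises only if some samples are classed as fasting, the SI column drives the flag, and a child has a value from 126 to just under 200 mg/dL.

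The calcium discrepancy is real but small and fits truncation. The creatinine gap (176.8 against 176) and the changes of inequality sign are matters of tidiness.

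The consequence is confined to one descriptive safety table. No efficacy or inferential result is touched. The point is still worth acting on before database lock, because a pre-specified safety threshold should give one answer and the correction is cheap.

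**What to change.** 1. Reconcile the two columns of Appendix 14.4, starting with the upper fasting-glucose limit and then calcium. The sponsor should confirm which figures are intended; this review does not choose the clinical limit.
2. Add one sentence to SAP Section 8.6 naming the unit system from which the flags are derived. Alternatively, define each SI limit as the unrounded conventional limit times the factor, with the same inequality sign. That rule should also cover random glucose, BUN and creatinine.
3. If SI limits are kept, avoid a rounded figure for fasting glucose. SAP Section 3 rules out rounding before analysis, and 126 mg/dL converts to 6.994, so a limit of ≥ 7.0 would miss a value of exactly 126.
4. State which glucose row applies to the samples collected, and how fasting status is determined if the fasting row is used.
5. Check the unit labels for calcium, BUN and glucose against the source document.

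The cost is a few appendix entries and two sentences in the SAP. No change to data collection is needed unless the sponsor wants to use the fasting row and fasting status is not already recorded.

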14.5 Vital Signs Criteria for Markedly Abnormal Values

Parameter (unit)	Age (years old)	Markedly Low	Markedly High
SBP (supine, standing) (mmHg)	6-12	Value \leq 70 and \geq 20 decrease from baseline	Value \geq 120 and \geq 20 increase from baseline
	13-18	Value \leq 90 and \geq 20 decrease from baseline	Value \geq 135 and \geq 20 increase from baseline
DBP (supine, standing) (mmHg)	6-12	Value \leq 40 and \geq 15 decrease from baseline	Value \geq 80 and \geq 15 increase from baseline
	13-18	Value \leq 50 and \geq 15 decrease from baseline	Value \geq 90 and \geq 15 increase from baseline
Pulse rate (supine, standing) (bpm)	6-10	Value \leq 60 and \geq 15 decrease from baseline	Value \geq 135 and \geq 15 increase from baseline
	11-18	Value \leq 50 and \geq 15 decrease from baseline	Value \geq 120 and \geq 15 increase from baseline
SBP orthostatic criteria (mmHg)	~	\geq 20 decrease from supine to standing position	NA
DBP orthostatic criteria (mmHg)	~	\geq 10 decrease from supine to standing position	NA
Pulse rate orthostatic criteria (bpm)	~	NA	\geq 20 increase from supine to standing position
Temperature (°C)	~	NA	Value \geq 38.3°C and \geq 0.8°C increase from baseline

Note: ~ means that the abnormal range is applicable for all subjects within age group: 6 to 17 years old.

14.6 12-Lead ECG Criteria for Markedly Abnormal Values

ECG parameter (unit)	Age (years old)	Abnormally Low	Abnormally High
HR (bpm)	6 to <8	< 65	> 115
	8 to <12	< 55	> 110
	12 to <16	< 50	> 105
	≥16	< 50	> 100
PR interval (msec)	6 to <8	--	> 160
	8 to <12	--	> 175
	12 to <16	--	> 180
	≥16	--	> 200
QRS interval (msec)	6 to <8	--	> 100
	8 to <12	--	> 105
	12 to <16	--	> 110
	≥16	--	> 120

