4.2. Study Conduct Rationale

Dasotraline has been evaluated for the treatment of ADHD in 2 completed studies to date. An additional study was completed that evaluated the safety, tolerability, pharmacokinetic, and pharmacodynamic properties of dasotraline in pediatric (6 – 12 years) and adolescent (13 - 17 years) subjects with ADHD. In this multicenter, open-label study 105 subjects were assigned to single oral doses of dasotraline 1 - 16 mg in a dose-escalating manner. Dasotraline was characterized by slow absorption (median t_{max} was 9.6 to 12 hours) and elimination (median $t_{1/2}$ was 56 to 84 hours) in both pediatric and adolescent subjects. The change in C_{max} with dose was slightly greater than dose proportional. Increase in overall exposure (AUC) with dose was greater than dose proportional. Apparent oral clearance was highest in the lowest dose group relative to the higher dose groups. No deaths, serious adverse events (SAE), or discontinuations because of an adverse event (AE) were reported in this study. The most frequently reported AE by investigators were tachycardia (25 subjects; 23.8%) and electrocardiogram QT prolonged (5 subjects; 4.8%), nearly all of which were considered related to study drug and mild in severity. Tachycardia AEs were reported in both age groups and in every dose cohort. Most events of tachycardia were reported on the day of study drug administration. No subjects experienced QT prolongations > 500 msec. Based on the centrally read electrocardiogram (ECGs) in the study, no clinically significant trends were identified within the ECG results.

Blood pressure increased, blood pressure systolic increased, blood pressure orthostatic abnormal, and orthostatic hypotension AEs were reported in 1 subject each. Overall, after dosing, 90 subjects (85.7%) met predefined criteria for orthostatic tachycardia and 40 (38.1%) met predefined criteria for orthostatic hypotension.

A completed study evaluated the efficacy and safety of 2 doses of dasotraline (4 mg/day and 8 mg/day) in adult subjects with ADHD. In this 4-week, double-blind, placebo-controlled study, dasotraline (8 mg/day) was found to be safe and effective for the treatment of adult subjects with ADHD.

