8.8 Vital Signs

Vital signs, including respiratory rate; body temperature; supine, standing, and orthostatic blood pressure; supine, standing, and orthostatic heart rate; BMI; and body weight, will be measured at all scheduled in-person study visits (Screening [Visit 1 and Visit 2], Visit 4, Visit 5, and EOS [Visit 6]).

Supine systolic blood pressure, standing systolic blood pressure, orthostatic systolic blood pressure, supine diastolic blood pressure, standing diastolic blood pressure, orthostatic diastolic blood pressure, supine heart rate, standing heart rate, orthostatic heart rate, respiratory rate, body temperature, body weight, and BMI will be summarized descriptively for each visit by treatment group for the absolute value and change from baseline values using descriptive statistics.

In addition, the incidence of sponsor-defined markedly abnormal post-baseline vital sign values will be presented to examine the frequency and percentage of subjects that meet the PCS criteria outlined in Appendix 14.5.

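### The three orthostatic criteria in SAP 14.5 have no baseline condition, so children who already met them before drug are counted as post-baseline abnormalities, which dilutes the arm ratio and does not show which cases are new

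*SAP*

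**What the plan says.** SAP 14.5 defines markedly abnormal vital signs. For supine and standing systolic pressure, diastolic pressure and pulse, each age band combines an absolute limit with a change from baseline; the high systolic rows, for instance, end with a condition of at least "20 increase from baseline". Temperature follows the same pattern, with at least "0.8°C increase from baseline" on top of the absolute limit.

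The orthostatic rows are built differently. The systolic (20 mmHg) and diastolic (10 mmHg) rows need only a "decrease from supine to standing position", and the pulse row (20 bpm) only an "increase from supine to standing position". None refers to baseline.

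SAP 8.8 says how the criteria are used: "the incidence of sponsor-defined markedly abnormal post-baseline vital sign values will be presented", as number and percentage of subjects. It does not say how to treat a child who met a row before the first dose. The same section also plans summaries of orthostatic pressures and heart rate, which "will be summarized descriptively for each visit by treatment group for the absolute value and change from baseline values".

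Protocol 4.2 gives the only orthostatic rates in the documents. In an open-label single-dose study of 105 children and adolescents, after dosing, "90 subjects (85.7%) met predefined criteria for orthostatic tachycardia and 40 (38.1%) met predefined criteria for orthostatic hypotension". The thresholds are not stated and no placebo arm is described.

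**The concern.** An orthostatic row compares two postures at one visit. It does not compare the child on drug with the same child off drug. A child whose pulse rises by 20 bpm on standing on Day 1, before any capsule, and does so again on Day 15, enters the table as a post-baseline abnormality in whichever arm he or she is in.

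Elsewhere the SAP separates new findings from old ones. Medical-history events count as treatment-emergent only if they worsen (SAP 8.4), neurological findings get a shift table from baseline (8.7), and QT intervals get change-from-baseline categories (8.9). Orthostatic abnormality has no such subject-level rule.

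The point is worth attention because tachycardia was the most frequent adverse event in the single-dose study (25 subjects, 23.8%), and a large share of its subjects met orthostatic criteria after dosing. If many children also meet the SAP rows before drug, the planned percentages are partly made up of children on whom the drug had no orthostatic effect.

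**Working it through.** **Row check of SAP 14.5.** Orthostatic rows without a baseline term: 3 of 3. Other blood-pressure, pulse and temperature rows without one: 0.

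**The protocol's own figures.** 90/105 = 85.7% and 40/105 = 38.1%, both as stated. They are post-dose rates.

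**Inputs for the illustration.** From the documents: about 55 children per arm (Protocol 7.2.1). Assumed, because the documents are silent:
- *b*, the share meeting a row before drug, from 10% to 85.7%. The upper values borrow the post-dose rates only as points on a range;
- *s*, the share of those still meeting it after baseline: 100%, then 70%, equal in both arms;
- *q*, new onset among children negative at baseline: 10% on placebo and 30% on drug, a true risk ratio of 3.0.

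**Formulas.** Planned count: b·s + (1 − b)·q. New-onset count over all treated children: (1 − b)·q.

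Example at b = 20%, s = 100%. Planned: placebo 0.20 + 0.80 × 0.10 = 28.0%; drug 0.20 + 0.80 × 0.30 = 44.0%; ratio 1.57; difference 16 points. New onset: 8.0% and 24.0%; ratio 3.0; difference 16 points.

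| Background b | Planned count, placebo vs drug | Ratio | New onset, placebo vs drug | Ratio | Difference, either count | Pre-drug positives as share of drug-arm planned count |
|---|---|---|---|---|---|---|
| 10% | 19.0% vs 37.0% | 1.95 | 9.0% vs 27.0% | 3.0 | 18 points | 27% |
| 20% | 28.0% vs 44.0% | 1.57 | 8.0% vs 24.0% | 3.0 | 16 points | 45% |
| 38.1% | 44.3% vs 56.7% | 1.28 | 6.2% vs 18.6% | 3.0 | 12.4 points | 67% |
| 85.7% | 87.1% vs 90.0% | 1.03 | 1.4% vs 4.3% | 3.0 | 2.9 points | 95% |

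With s = 70% the planned-count ratios are 2.12, 1.73, 1.38 and 1.05.

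**Bias of the difference.** The term b·s is the same in both arms and cancels, so the absolute difference is identical under the two counts.

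**Precision.** The planned proportions carry the variability of the background as well. As an index only, since SAP 8.2 makes safety descriptive, the approximate power of a two-sided 5% comparison with 55 per arm and full persistence is:

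| Background b | Planned count | New-onset count, all treated as denominator |
|---|---|---|
| 10% | 56% | 70% |
| 20% | 42% | 63% |
| 38.1% | 25% | 51% |
| 85.7% | 7% | 14% |

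**The case against.** **A reader might infer that the table hides a drug effect.** It does not. Randomization gives both arms the same expected background, placebo displays it, and the difference over all treated children is unchanged. A contrast such as 3 points in the planned table against 20 points among baseline-negative children compares two denominators. At b = 85.7%, about 55 × 0.143 = 7.9 children per arm are baseline-negative; 20% of them is about 1.6 children, and 1.6/55 is the same 2.9 points. The added line finds no extra cases.

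**A reader might take 85.7% as the background and conclude that the table sits at its ceiling.** The documents do not support that. The figure is post-dose, from single doses of 1 to 16 mg in an age range reaching 17 years, under unstated criteria. If much of it was drug effect, the background is low and dilution is modest. The hypotension figure, 38.1%, is far from a ceiling even if all of it were background; the illustration still shows 12.4 points there.

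**Other planned output helps.** Mean change from baseline in orthostatic values is summarized by arm (SAP 8.8), and all data are listed by subject and time point (SAP 3), so new cases could be picked out by hand. Tachycardia as such is also covered by the supine and standing pulse rows, which do have a baseline condition. Table specifications are in separate documents not seen here (SAP 1).

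**The orthostatic rows have an internal comparator**, the supine reading at the same visit, and the laboratory limits (14.4) and ECG limits (14.6) also lack a baseline condition.

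Most of this stands and limits the point. What remains is that a postural comparator is not a pre-drug comparator. Means do not count affected children, and a listing is not a summary by arm.

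**Conclusion.** The reading of SAP 14.5 and 8.8 holds: pre-existing orthostatic responders are counted as post-baseline abnormalities, and among the blood-pressure, pulse and temperature criteria only the orthostatic rows allow this. The consequence is limited to the incidence table. The ratio between arms is pulled toward 1, new-onset abnormality is measured less precisely, and the table does not show which positives are new. The absolute difference is not biased, provided that background and persistence are equal in the two arms.

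The size cannot be fixed from the documents, because no pre-drug rate is given. Under the stated assumptions a true ratio of 3.0 appears as 1.95 at a 10% background and 1.03 at 85.7%. Some dilution occurs at every background tested. No efficacy result and no planned test is affected. This is a cheap improvement.

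**What to change.** Before unblinding, amend SAP 8.8 and 14.5 as follows:

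- Keep the three orthostatic criteria and the any-post-baseline count as planned. That count also captures any drug effect on whether a pre-existing response persists, which a new-onset line would miss.
- Name the vital-sign baseline visit, for example Day 1 before the first dose. The SAP identifies Visit 4 as baseline for the SKAMP outcome (7.4.1) but not for vital signs, which are taken before drug at Visits 1, 2 and 4.
- For each orthostatic row, add one line by arm: children meeting it post-baseline but not at baseline. An equivalent baseline-by-post-baseline shift table would serve. State whether the denominator is all treated children or those negative at baseline.

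No new data are needed. Supine and standing readings are part of the standard vital-sign procedure (Protocol 11.4.3) and are scheduled on Day 1, with dosing starting that evening, and on Day 15.

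The cost is one extra table line per criterion and, if baseline-negative children are the denominator, a smaller one: at 55 per arm, about 50 children at a 10% background, 34 at 38.1% and 8 at 85.7%. If Day 1 is chosen, baseline status rests on a single supine/standing pair, so some children will be misclassified; a footnote should say so.
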